18.	Reference.....	43

1. Synopsis

Trial Title	A Phase 1, Dose-Escalation Study to assess the Safety and Immunogenicity of a COVID-19 Vaccine GRAd-COV2 in Healthy Adults and Elderly Subjects	
Internal ref. no.	RT-CoV-2	
Clinical Phase	Phase I	
Trial Centre	Istituto per Malattie Infettive (INMI) L. Spallanzani, [name]; Coordinator Clinical Site Centro Ricerche Cliniche Verona srl c/o Policlinico G.B. Rossi [name]	
Trial Design	Open label study	
Trial Participants	(i) Healthy adult volunteers (aged 18-55) including men and non-pregnant women (ii) Elderly volunteers (aged 65-85) without significant clinical conditions	
Planned Sample Size	Arm 1: 15 Healthy younger adults volunteers (aged 18-55); 1 dose GRAd-COV2 (5×10^{10} vp) Arm 2: 15 Healthy younger adults volunteers (aged 18-55); 1 dose GRAd-COV2 (1×10^{11} vp) Arm 3: 15 Healthy younger adults volunteers (aged 18-55); 1 dose GRAd-COV2 (2×10^{11} vp) Arm 4: 15 Healthy older adults volunteers (aged 65-85); 1 dose GRAd-COV2 (5×10^{10} vp) Arm 5: 15 Healthy older adults volunteers (aged 65-85); 1 dose GRAd-COV2 (1×10^{11} vp) Arm 6: 15 Healthy older adults volunteers (aged 65-85); 1 dose GRAd-COV2 (2×10^{11} vp) Total = 90 volunteers	
Study duration	12 months	
Follow up duration	Patients will be followed up for 24 weeks after vaccination. Follow-up will include medical visit and test at day 2, day 7, week 2, week 4 week 8, week 12 and week 24	
Planned Trial Period	10 months (from screening of first participant to 6 months after final vaccination of last volunteer)	
	Objectives	Endpoints
Primary	To evaluate the safety of administering GRAd-COV2, intramuscularly in healthy (younger and older adults) volunteers	A. Occurrence of solicited local AE signs and symptoms for 7 days following the vaccination B. Occurrence of solicited systemic AE signs and symptoms for 7 days following the vaccination C. Occurrence of unsolicited AE for 28 days following the vaccination D. Change from baseline for safety laboratory measures at different time point E. Occurrence of severe AE during the whole study duration

Secondary	To assess the cellular and humoral immune response to SARS-CoV2 elicited by the vaccine	A. CLIA to quantify antibodies to SARS-CoV-2 S-protein (anti-S-Ab) B. CLIA to quantify antibodies to SARS-CoV-2 nucleocapsid protein (anti-N-Ab) C. SARS-CoV-2 micro-neutralization assay to quantify neutralizing antibody activity to the virus D. Ex vivo IFN-gamma ELISpot responses to SARS-CoV-2 S-protein
Investigational Medicinal Product	Replication-defective gorilla adenovirus (GRAd) encoding prefusion-stabilized SARS-CoV-2 S-protein protein, GRAd-COV2	
Formulation, Dose, Route of Administration	Liquid, intramuscular needle injection	

2. Abbreviation

Ad	Adenovirus
AE	Adverse event
AR	Adverse reaction
ChAd	Chimpanzee Adenovirus
CI	Chief Investigator
CLIA	Chemiluminescent immunoassay
CMV	Cytomegalovirus
COVID-19	Coronavirus disease which is caused by SARS-CoV-2
CRF	Case Report Form
CT	Clinical Trials
CTA	Clinical Trials Authorisation
DNA	Deoxyribonucleic acid
DSMB	Data Safety Monitoring Board
DSUR	Development Safety Update Report
EC	Ethics Committee
ECG	Electrocardiogram
ELISpot	Enzyme-linked immunosorbent spot
GCP	Good Clinical Practice
GMO	Genetically Modified Organism
GP	General Practitioner (Medico di Medicina generale)
GRAd	Gorilla Adenovirus
HLA	Human Leukocyte Antigen
IB	Investigators Brochure

ICF	Informed Consent Form
ICH	International Conference on Harmonisation
IMP	Investigational Medicinal Product
IFN- γ	Interferon Gamma
N-protein	Nucleocapside protein
PBMC	Peripheral Blood Mononuclear Cell
PIL	Participant Information Leaflet
RNA	Ribonucleic acid
S-protein	Spike protein
SAE	Serious Adverse Event
SAR	Serious Adverse Reaction
SARS-CoV-2	Severe acute respiratory syndrome coronavirus 2
SFC	Spot-Forming Cells
SOP	Standard Operating Procedure
SUSAR	Suspected Unexpected Serious Adverse Reactions
TMF	Trial Master File
vp	Viral Particles
WHO	World Health Organisation

3. Background information and rationale

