4.2. Endpoints

4.2.1. Primary endpoints (safety)

The primary endpoint of the study is to assess safety in term of occurrence of solicited and unsolicited adverse events (AE). Occurrence of AE will be monitored by preplanned medical visits and blood tests (active surveillance) and by recording participant's reported AE (passive surveillance). This includes:

- A. Occurrence of solicited local AE signs and symptoms for 7 days following the vaccination
- B. Occurrence of solicited systemic AE signs and symptoms for 7 days following the vaccination

- C. Occurrence of unsolicited AE for 28 days following the vaccination
- D. Change from baseline for safety laboratory measures at different 2 days, 7 days, 2 weeks, 4 week, 8 weeks, 12 weeks and 24 weeks
- E. Occurrence of serious AE (SAE) during the whole study duration

Volunteers will undergo clinical follow up for AE for 24 weeks following completion of the vaccination regimen. SAEs will be collected throughout the study.

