8.3. Administration of Investigational Medicinal Products

The dosages of GRAd-COV2 to be used in this study are: 5×10^{10} vp (low dose), 1×10^{11} vp (intermediate dose) and 2×10^{11} vp (high dose). See the SOP for detailed information on the preparation, labeling, storage, and administration of the GRAd-COV2 investigational vaccine. For administration of the high dose, 1ml of GRAd-COV2 will be injected without dilution. For intermediate and low dose, the vaccine will be diluted in sterile saline solution to reach a final 1ml injection volume. Vaccine dilution will be performed by the site pharmacist on the same day of vaccine administration.

On vaccination day, GRAd-COV2 will be allowed to thaw to room temperature and will be administered within 1 hour of removal from the freezer. The vaccine will be administered intramuscularly into the deltoid of the non-dominant arm (preferably). Qualified medical personnel will wear gloves. All volunteers will be observed in the unit for 4 hours (± 10 minutes) after vaccination. During administration of the investigational products, Advanced Life Support drugs and resuscitation equipment will be immediately available for the management of anaphylaxis. Vaccination will be performed and the IMPs handled according to the relevant SOPs.

The study will be performed in accordance with Genetically Modified Organisms (Contained Use) Regulations (2001/18/CE). In order to minimize dissemination of the recombinant vectored vaccine virus into the environment, inoculation sites will be covered with a dressing after immunization. This should absorb any virus that may leak out through the needle track. The dressing will be removed from the injection site after 30 minutes (+15/- 5 minutes) and will be disposed as GMO waste by autoclaving.

9. Adverse event assessment and management

Safety will be assessed by the frequency, incidence and nature of adverse events and severe adverse events arising during the study.

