9.1. Definitions

Adverse event (AE). (AE) is any untoward medical occurrence in a participant, which may occur during or after administration of the vaccine and does not necessarily have a causal relationship with the intervention. An AE can therefore be any unfavorable and unintended sign (including an abnormal laboratory finding), symptom or disease temporally associated with the study intervention, whether or not considered related to the study intervention.

Adverse reaction (AR). An AR is any untoward or unintended response to the vaccine. This means that a causal relationship between the vaccine and an AE is at least a reasonable possibility, i.e., the relationship cannot be ruled out. All cases judged by the reporting medical Investigator as having a reasonable suspected causal relationship to the vaccine (i.e. possibly, probably or definitely related to the vaccine) will qualify as adverse reactions.

Unexpected adverse reaction (UAR). An UAR is any untoward or unintended response to the vaccine, the nature and severity of which is not consistent with the information about the medicinal product in question set out in the investigator brochure (IB) or summary of product characteristics.

Serious adverse event (SAE). A SAE is an AE that results in any of the following outcomes, whether or not considered related to the study intervention.

- A. Death
- B. Life-threatening event (i.e., the participant was, in the view of the Investigator, at immediate risk of death from the event that occurred).
- C. Persistent or significant disability or incapacity (i.e., substantial disruption of one's ability to carry out normal life functions).
- D. Hospitalization, regardless of length of stay, even if it is a precautionary measure for continued observation.
- E. Significant medical intervention including surgery or administration of drugs (examples of such medical events include allergic reaction requiring intensive treatment in an emergency room or clinic, blood dyscrasias, or convulsions regardless eventual need of hospitalization)
- F. A grade ≥ 3 abnormalities on safety blood test according to Common Terminology Criteria for Adverse Events (CTCAE v.4 and MedDRA 12.1).

Serious adverse reaction (SAR). A SAE (expected or unexpected) that, is in the opinion of the reporting Investigator, believed to be possibly, probably or definitely due to the vaccine.

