9.5. Reporting procedure for all AE

All local and systemic AEs occurring in the 28 days following each vaccination observed by the Investigator or reported by the participants, whether or not attributed to study medication, will be recorded. Recording and reporting of all AEs will be detailed in SOP. All AEs that result in a participant withdrawal from the study will be followed up until a satisfactory resolution occurs or until a non-study related causality is assigned (if the participant consents to this). SAEs will be collected throughout the entire trial period (i.e. until W24).

SAEs will be reported on the SAE forms by doctors who enrolled participants to the principal investigator and DSMB. SAE will be documented accurately and notified within 48 hours to the DSMB. The DSMB will also review severity and causality analysis within 2 days and will provide advice on study continuation. AEs will be reported to DSMB within 7 days. In special circumstance the chair of DSMB may decide to involve the ethical committee to analyze AE reports in order to define how to continue the study.

SAR and SUSAR that occur within week 10 of the study will determine a temporal suspension of the enrollment pending the decision of DSMB. The suspension is decided by the local investigator and immediately communicated to principal investigator and DSMB. When a SAR or a SUSAR occurs among participants enrolled in a clinical center the investigator of the clinical center will immediately contact the principal investigator who will eventually contact other enrolling centers.

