An overview will be provided with the number and percentage of subjects as well as the total number of occurrences of the following event categories by treatment group:

- Any TEAE;
- Any TEAE related to study drug;
- Any treatment-emergent SAE (see section [4.11.2](#));
- Any treatment-emergent SAE related to study drug;
- Any TEAE leading to study discontinuation;
- Any AESI;
- Any solicited adverse reactions emerged in the first 7 days post dose.

Adverse event summaries by system organ class (SOC) and preferred term (PT) with number and percentage of subjects as well as the total number of occurrences will be provided by treatment group for the following:

- All TEAE;
- TEAEs by maximum severity;
- TEAEs by causality;
- All AESI;
- All solicited adverse reactions emerged in the first 7 days post dose.

Additional summary for all TEAE will be provided by PT and treatment group.

Adverse event summaries will be ordered in terms of decreasing frequency for SOC and PT within SOC in the Total group and then alphabetically for SOC and PT within SOC. Summaries will be ordered in terms of decreasing frequency for PT in the Total group in summaries where SOC is not included.

For each subject and each adverse event, the worst severity recorded will be attributed and used in the by-severity summaries. Similarly, the worst causality (most related to treatment) will be attributed and used in the by-causality summaries. If severity or causality is missing, a conservative approach for AE assessment (taking into account the worst case) will be followed.

By-subject listing of all adverse events (including non-treatment-emergent events) will be provided by treatment group. Adverse event listing will include center, subject identifier, age, sex, race, adverse event (SOC, PT, and verbatim term), date of onset, date of resolution, duration, solicitation flag, special interest flag, severity, seriousness, action taken, outcome and causality.

Adverse event listings will be provided for the following:

- All AEs
- All severe TEAE;
- All TEAE related to study drug;
- All AESI;
- All solicited adverse reactions emerged in the first 7 days post dose.

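### Primary endpoint E is severe AEs in the synopsis but serious AEs in section 4.2.1, and the SAP tabulates neither by arm over the whole study

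*Protocol*

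**What the plan says.** The protocol synopsis and Protocol 4.2.1 both list five primary safety endpoints, A to E. In the synopsis, E is "Occurrence of severe AE during the whole study duration". In 4.2.1 it is "Occurrence of serious AE (SAE) during the whole study duration". The opening of Protocol section 9 uses the synopsis term: "Safety will be assessed by the frequency, incidence and nature of adverse events and severe adverse events arising during the study".

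On the recording period, 9.5 requires recording of "All local and systemic AEs occurring in the 28 days following each vaccination observed by the Investigator or reported by the participants", with SAEs collected until W24. Section 4.2.1 says: "Volunteers will undergo clinical follow up for AE for 24 weeks following completion of the vaccination regimen".

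The SAP does not restate endpoint E. SAP 2.1 lists programme goals, and 3.2.1 names AE assessments only in general terms. SAP 4.11.1 defines a TEAE by onset or worsening within 28 days of dosing. It then specifies an overview that counts treatment-emergent SAEs, a table of TEAEs by maximum severity, and a listing headed "All severe TEAE". It also specifies a by-subject listing of all AEs, including those that are not treatment-emergent, with severity and seriousness shown. SAP 4.11.2 adds a listing of serious AEs.

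**The concern.** A primary endpoint has two definitions, and the protocol elsewhere treats the two words as different things. In the halting rules of 9.8, rules A and B turn on severe solicited events, while rules C and D turn on serious ones. A reader who takes the endpoint from the synopsis and one who takes it from 4.2.1 would count different events from the same database.

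The 28-day window fits primary endpoint C, "Occurrence of unsolicited AE for 28 days following the vaccination". The SAP applies it to its SAE count and its severity summaries as well, whereas endpoint E runs for the whole study under either wording. A final report built from the planned AE tables would therefore have no by-arm figure for endpoint E over its stated period, and readers would have to count from listings.

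**Working it through.** There is no sample-size or power figure to reproduce; the plan states that none was calculated. The check compares texts, plus one calculation of time covered.

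**Step 1. Are the two terms the same set?** Protocol 9.1 defines an SAE by outcome, and Table 1 grades severity mostly by measurement.

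- Severe, not necessarily serious: Table 1 grades fever above 39.0 as severe. It is serious only if a 9.1 criterion is also met.
- Serious, not necessarily severe: 9.1 counts "Hospitalization, regardless of length of stay, even if it is a precautionary measure for continued observation". Section 7.3 provides for hospital isolation of participants with COVID-like respiratory symptoms until a negative test, so a mild illness can become an SAE.
- In both sets: grade 3 or higher laboratory abnormalities (9.1, criterion F), and solicited reactions graded severe because they required hospitalization (9.2).

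The sets overlap but neither contains the other.

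**Step 2. What does the SAP produce for each reading?**

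| Output | Events | Period |
|---|---|---|
| AE overview (SAP 4.11.1) | Treatment-emergent SAEs | 28 days |
| AEs by maximum severity (4.11.1) | TEAEs | 28 days |
| Severe-AE listing (4.11.1) | TEAEs | 28 days |
| All-AE listing (4.11.1) | All AEs, with severity | No 28-day limit; by subject |
| SAE listing (4.11.2) | Serious AEs | No 28-day limit; by subject |
| AESI table (4.11.1) | Grade 3 or higher laboratory values | No 28-day limit stated |
| CTCAE grade table (4.11.3) | Laboratory values | By visit and overall |
| Vital-sign severity table (4.11.5) | Graded vital signs | By visit and overall |

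The first two rows are the by-arm AE summaries closest to endpoint E, and both stop at 28 days. The last three rows reach W24 but cover laboratory values and vital signs only.

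**Step 3. How much of the period is missed?** Follow-up is 24 weeks (synopsis; 9.5 ends SAE collection at W24).

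- Whole period: 24 × 7 = 168 days.
- Covered by the TEAE window: 28 / 168 = 16.7%.
- Not covered: (168 − 28) / 168 = 140 / 168 = 83.3%.
- With the W24 visit at its window limits of ±14 days: (154 − 28) / 154 = 81.8% to (182 − 28) / 182 = 84.6%.

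Of the seven post-vaccination visits (D2, W1, W2, W4, W8, W12, W24), three fall after day 28: W8, W12 and W24.

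**Step 4. Is AE information due after day 28?** Section 9.5 alone limits non-serious AEs to 28 days. Against it:

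- 4.2.1 requires AE follow-up for 24 weeks.
- 7.8 requires assessment of local and systemic AEs at W8, W12 and W24.
- Protocol Figure 9 and SAP Table 5 mark AE reporting at every visit to W24.
- 9.7 requires AEs to be registered and states no 28-day limit.

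This is a contradiction about the recording period. Sites that follow 9.5 and sites that follow the schedule could record different late events.

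**The case against.** The best reply is that severe in the synopsis is a slip for serious. The protocol uses the words loosely elsewhere: 9.1 defines a SUSAR as a severe reaction although the abbreviation list expands it as serious, and 9.7 gives SAEs, SARs and SUSARs as examples of severe or unexpected events. The two lists A to E are parallel, 4.2.1 adds the SAE abbreviation, and 9.5 collects SAEs to W24. The trial is descriptive, with no formal testing. A slip is the likelier explanation, and this shows which way to correct the text. It does not remove the contradiction from a primary endpoint, and it does not help the SAP, whose overview counts SAEs for 28 days only.

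Three stronger readings are tempting and are not supported.

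- A reader of 9.5 alone might infer that late severe, non-serious AEs need not be recorded at all. Sections 4.2.1, 7.8 and 9.7 and both schedules say otherwise.
- A reader might infer that the synopsis version cannot be delivered. AE reporting is scheduled to W24, and late AEs appear with their severity in the all-AE listing. What is missing is the by-arm summary. A temperature above 39.0 measured at a late visit would also enter the vital-sign severity table.
- A reader might want the number of events that fall between the two readings. The documents give no rate of severe or serious events, so any such number would be a guess.

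**Conclusion.** Wrong as written, as an internal inconsistency. Primary endpoint E has two definitions that select different events. Under either one, the SAP's by-arm AE tables cover 28 of 168 days and leave 140 days (83%) to by-subject listings for SAEs and for severe clinical AEs. Laboratory and vital-sign grades are not affected. Separately, 9.5 conflicts with 4.2.1, 7.8 and the schedules on the AE recording period.

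The percentage is a share of follow-up time. It does not estimate the share of events, which could be concentrated soon after vaccination. It assumes that the whole study means 24 weeks per participant, as the synopsis and 9.5 indicate.

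**What to change.** 1. State one term for endpoint E in the synopsis, in 4.2.1 and at the opening of section 9. Sections 4.2.1 and 9.5 point to serious AEs.
2. Reconcile 9.5 with 4.2.1, 7.8, Figure 9 and SAP Table 5, so that one recording period holds for non-serious AEs.
3. In SAP 4.11.1, add two by-arm rows covering vaccination to W24, any SAE and any severe AE, beside the existing 28-day TEAE rows. State which SAE definition the first row uses, because SAP 4.11.2 omits the protocol's laboratory criterion (9.1, F) and SAP 4.11.1 treats those values as AESI.

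If step 2 keeps a 28-day limit for non-serious AEs, footnote the severe-AE row to say that later collection was not complete.

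The cost is wording in a few protocol places and two table rows. AE reporting is already scheduled at every visit to W24, so no visit, sample or procedure is added.

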3.1. Coronavirus disease 2019 current situation

Severe Acute Respiratory Syndrome Coronavirus 2 (SARS-CoV-2) is associated with a new diverse clinical syndrome called Coronavirus disease 2019 (COVID-19). Common symptoms of COVID-19 include fever, cough, shortness of breath and dyspnea that may eventually progress towards acute respiratory distress syndrome and death. About 80% of patients have mild to moderate disease, 14% have severe disease and 6% are critical (namely, they develop respiratory failure, septic shock, and/or multiple organ dysfunction/failure). The severity of clinical presentation is directly dependent on patients' age. Infections needing hospitalization are exceptional events among children younger than 10 years while the case-fatality rate can exceed 10% among people older than 70 years. [1,2]

The COVID-19 pandemic originated in Wuhan, China, in early December 2019. The World Health Organization declared the outbreak a Public Health Emergency of International Concern on 30 January by on 11 March it has been recognized as the cause of the biggest pandemic event over the last century. [2,3]

The first cases reported in Italy were two Chinese tourists who were identified in Rome on January 29th.[4] Due to the prompt intervention of Regional Infection Control network, neither of these cases did actually produce independent cluster. However, the epidemic sprung in the North of the country since the beginning of February when eleven municipalities were locked down. As for other countries, the Italian government implemented a series of strict collective measures for the control of local transmission. On March 11th, the government enforced a law to stop nearly all commercial activities except for supermarkets and pharmacies.

[5] On March 21st, the quarantine was strengthened, all non-essential businesses were stopped and people's movement severely restricted. [6] These collective measures adopted in the first phase of the epidemic, have contributed decisively to the flattening of the epidemic curve with a reduction in new cases and a consequent lightening of the health care burden. Although these measures made it possible to overcome the emergency phase, in another respect they had deleterious impact on economics and social life, which can be unsustainable in the medium-long term. Therefore, Italy, like many countries in Europe, has been easing collective measures in favor of a progressive recovery of the economic and social life. [7] However, due to the still low level of immunity of the population, a rapid resumption of sustained transmission in the community may occur. [8] There are three main strategies for controlling the spreading of a new emergent pathogens during a massive event such as the current COVID-19 pandemic.

Firstly, implementing and strengthening of a robust surveillance system that it is capable of promptly identifying and of properly managing incident cases and their contacts in order to intercept local clusters and curb the subsequent epidemic waves. [9]

Secondly, endorsing research on new drugs with high direct antiviral activity that can be used either to prevent infection in high-risk individuals (pre-exposure prophylaxis), prevent infection in exposed people (post-exposure prophylaxis) or care infected people in order to curb their capability to transmit the infection and prevent clinical progression toward severe diseases. [10]

Finally develop effective vaccine strategies for either preventing infection in general population or, at least, preventing severe clinical presentation diseases in frailest subjects. [11]

Here we propose a program for rapidly scale up a new investigational vaccine based on an innovative simian adenoviral vector. The study design has been tailored on currents needs of Italy and it is aimed at rapidly demonstrating safety and immunogenicity of a single vaccine administration at escalating doses either in healthy adult or elderly people. The results of the study will be eventually implemented into phase 2/3 clinical trial designed to meet the immediate need of those groups of people at the highest risk of severe COVID-19

3.2. The emergent SARS-CoV-2 virus and the choice of S-protein protein as vaccine antigen

SARS-CoV-2 belongs to the broad family of viruses known as coronaviruses. It is a lipid enveloped virus sizing approximately 100–120 nM, and the inner nucleocapsid houses the single-stranded non-segmented positive-sense RNA genome (ssRNA+). SARS-CoV-2 is the seventh known coronavirus that can be transmitted human-to-human, after 229E, NL63, OC43, HKU1, MERS-CoV, and the original SARS-CoV. As other SARS-like coronavirus, including MERS and SARS, SARS-CoV-2 is a member of the subgenus Sarbecovirus (beta-CoV lineage B) and has been associated with severe clinical presentation in human beings. SARS-CoV-2 genome is approximately 30,000 bases in length. SARS-CoV-2 is unique among known betacoronaviruses in its incorporation of a polybasic cleavage site, a characteristic known to increase pathogenicity and transmissibility in other viruses. [12] It is believed that SARS-CoV-2 has zoonotic origins due to close genetic similarity to bat coronaviruses, suggesting it emerged from a bat-borne virus. There is no evidence yet to clarify the animal-human interface, including an animal species or special environmental conditions to link the virus natural reservoir and its introduction to human communities. However, the little genetic diversity among current SARS-CoV-2 strains suggest that the spillover event might have been occurred in late 2019. [13]

Like other coronaviruses, SARS-CoV-2 has four structural proteins, known as the S (S-protein), E (envelope), M (membrane), and N (nucleocapsid) proteins (Figure 1); the N protein holds the RNA genome, and the S, E, and M proteins together create the viral envelope. Coronavirus S-protein (S) and nucleocapsid (N) envelope proteins are highly immunogenic and constitute important antigenic targets for the development of serologic assays. [14]

The S-protein has a pivotal central role in viral infection and pathogenesis. S-protein is, in fact, the central element for allowing the virus to attach to and fuse with the membrane of a host cell; specifically, its S1 subunit catalyzes attachment, the S2 subunit fusion. [15-16]

[figure not shown]

Figure 1 The SARS-CoV-2

Recent evidence suggest that anti-S neutralizing antibodies from sera of COVID-19 convalescent patients can prevent cell infection in vitro by blocking viral binding to ACE2 and the eventual formation of syncytia.[17-18]

SARS-CoV-2 cell-adhesion and cell-entry is a complex mechanism. Functional S-protein has a dimeric structure including 2 subunits (S1 and S2). Cleavage of S-protein into the functional dimer is mediated by attachment of the S1 RBD to the ACE2 enzyme which exposes a cleavage site on S2 that is acted on by host cell proteases to initiate the process of cellular entry. Although SARS-CoV also uses the ACE2 receptor, SARS-CoV2 has a distinct furin cleavage site, not found in SARS-CoV, which may explain some of the biological differences. In fact, removal of this motif affects cellular entry: the furin cleavage site expands the versatility of SARS-CoV-2 for cleavage by cellular proteases and potentially the tropism and transmissibility owing to the wide cellular expression of furin proteases especially in the respiratory tract. [19-20]

The critical role of the S-protein, both in infection and pathogenesis process suggest that it is an attractive target for both for new drugs and vaccinations.

